## Secondary Endpoint Analysis and Statistical Considerations:

As described above for primary outcome measures, descriptive statistics will be determined for each composite and individual component measures of the TAND Checklist, VABS, Bayley-4, PLS-5 and ADOS-2 for neurodevelopment and behavior; EEG for electrophysiological connectivity; and dMRI for structural connectivity.

EEG data for conventional analysis (interictal and ictal epileptiform activity) will be sampled at 500 samples/channel/second, 0.5 Hz low pass and 100 Hz high pass filters, and a 60 Hz notch filter, with impedance less than 5 Kohm for all electrodes. Persyst software (San Diego, CA) will be used to digitally view each tracing by a single central reader in the standard timescale of 30 mm/sec and standard filter settings of 1 Hz low-frequency filter (high pass) and 70 Hz high frequency (low pass), along with a 60 Hz notched filter. EEG will be classified according to age-appropriate norms, as either normal or abnormal. Conventional EEG abnormalities will be further evaluated in terms of the presence or absence of background abnormalities, such as generalized or focal slowing, epileptiform discharges (focal, regional, bilateral, or generalized spike or spike and wave discharges), hypsarrhythmia (classic or modified), voltage attenuation, as well as clinical and/or electrographic seizures, in accordance with the NINDS common data element tools for epilepsy. The association between epileptiform discharges and primary efficacy outcome measures will be analyzed using multiple methods, including time-to-event

Version: 7.0\_11May2022

survival analysis, multivariable Cox proportional hazard analysis to assess the contribution of concurrent clinical or genetic variables on the response to treatment, and logistical regression analysis to determine the strength of associations.

EEG data for quantitative analysis (power, coherence, path length, clustering, and global efficiency) will be imported into Brain Vision Analyzer (BVA) software (Brain Products GmbH) to remove offsets, optimize scaling, and re-reference the data into the desired montage. The power spectral density of the artifact-free bipolar pair EEG data will be calculated using the fast Fourier transform (FFT) function. The 512-point FFT is calculated for artifact-free two-second epochs with a rectangular window, DC de-trending applied to each segment of data, 0.5 Hz overlap at the limits of the band, and yielding a frequency resolution of 0.5Hz. Power will be calculated in six frequency bands, corresponding to delta (0.5-4Hz), theta (4-8Hz), alpha (8-12Hz), beta (12-20Hz), gamma (30-50Hz), ripple frequencies (100-250Hz), and fast ripple frequencies (250-500Hz).

Supplementation of traditional DTI from dMRI data with DCI allows us to characterize changes in free water content, multiple oriented fascicles per voxel, and diffusivity parameters per fascicle, using the concepts of statistical modelling of infinitesimal microenvironments, and the well-established minimum requirements for compartment models. DIAMOND is a finite mixture model of compartments, where the signal arising from each of the compartments is represented by a statistical distribution of 3-dimensional infinitesimal microenvironments. Our model order selection algorithm determines from the dMRI data, exactly the number of compartments that are present at each voxel. DCI enables better delineation of white matter pathways relevant to CNS disease in TSC; allows measurement of the free water volume and improves compensation for partial volume averaging; provides increased sensitivity to detect loss of microstructural integrity; provides intra-voxel orientational heterogeneity and allows tractography of all fascicle orientations; and provides measures of diffusivities from the imaging data.

Sirolimus (TAVT-18) dosing and corresponding trough levels for the sirolimus (TAVT-18) treatment group will be analyzed for dose-dependent relationships to primary efficacy and safety outcome measures. We will define the developmental trajectory of sirolimus (TAVT-18) in very young infants ('projected model' line) using actual and dose-normalized sirolimus (TAVT-18) dose and corresponding trough concentrations at each sampling time, as done previously in patients with congenital vascular anomalies. We will then use validated population modeling approaches supported by the U.S. Food and Drug Administration to simulate drug-treated patient populations of interest. Mixed (random and fixed) effects modeling approach where the data are pooled with individual subject characteristics and maintained during the analysis will be employed to capture both inter-patient and intra-patient (also known as residual) variability. Exploratory covariate analyses using PK/PD modeling approach will be performed with variables considered to include (but are not limited to) age, gender, ethnicity, total bodyweight (TBW), body mass index (BMI), body surface area (BSA), hematocrit, disease status, time since last feeding, and concomitant medications. The fit of the population PK and PK/PD models will be evaluated both graphically and statistically. The final model will then be developed by applying a direct-link model to describe sirolimus concentrations and changes in primary efficacy and safety outcome measures to identify optimal dosing range for preservation of observed treatment effect compared to treatment-associated risk of AE.

Our consortium is actively involved in the NIH-funded epilepsy prevention clinical trial evaluating the pre-emptive treatment with vigabatrin in TSC infants (PREVeNT). The current study design is purposefully similar to that trial (age at time of enrollment, clinical epilepsy and neurodevelopment assessments between 0-12 months of age, timing of serial blood and EEG acquisitions). The underlying premise of the two studies, however, is distinct. PREVeNT specifically targets early epileptogenesis with a conventional anticonvulsant, vigabatrin, that is initiated *after* EEG abnormalities are identified. In contrast, the present study initiates treatment *after* TSC diagnosis, as the proposed treatment (sirolimus) targets the underlying molecular defect caused by genetic mutation of *TSC1* or *TSC2* that is present from birth. Thus, we will be able to directly compare outcome measures and biomarkers to explore the significance of timing (*before* vs. *after* EEG change) and mechanism (targeting the mTOR pathway vs. GABAnergic effect of vigabatrin) to prevent epilepsy onset and progression in TSC infants.

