## **2 BACKGROUND & RATIONALE**

A key intracellular signaling pathway regulated by the mechanistic target of rapamycin (mTOR), essential for normal cell growth, differentiation, metabolism, function, and survival is responsible for many of the clinical manifestations of Tuberous Sclerosis Complex (TSC). In the brain, subependymal giant cell astrocytomas (SEGA) arise from subependymal nodules in 10-15% of children with TSC and if untreated, can cause obstructive hydrocephalus. Even more common in TSC is epilepsy, affecting 80-90% of affected individuals. Seizures often present before 1 year of age as infantile spasms or focal seizures and too often is refractory to all available treatments and interventions. Seizures in general and infantile spasms particularly have additional devastating impact on neurodevelopment and long-term cognitive and behavioral outcomes. This is consistent with preclinical mouse models of TSC, in which seizures begin early and gradually worsen over time, to the point of intractability and early demise. TSC mouse models also demonstrate cognitive and behavioral deficits similar to the human disease. In each case, deficits could be reversed and/or prevented with preemptive everolimus or sirolimus (rapamycin) treatment, small molecule pharmacological inhibitors of mTOR.

Recent data from the NIH-funded TSC Autism Centers of Excellence Network (TACERN) not only confirms that 70% of diagnosed infants will develop seizures in the first year of life, but also that standardized, validated assessment tools at 12 month of age are able to identify measurable deficits in learning and behavior linked to early onset epilepsy in this population.  *Furthermore, infants who do not develop seizures or whose seizures are completely or relatively controlled by 12 months of age are much more likely to develop normally through 24 months of age and beyond*. Unfortunately, such infants are the minority in TSC. The cumulative preclinical and clinical evidence strongly support targeted anti-epileptogenic therapies for TSC and such disease modifying, preventative treatment should be initiated before the onset of seizures in the first year of life before epilepsy becomes refractory to conventional treatment and before epilepsy-associated neurocognitive and behavioral deficits take hold.

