## **5 STUDY DESIGN AND ORGANIZATION**

This trial originally planned to use a two stage, phase I clinical trial design, with the first stage to employ an open-label clinical trial design to verify dosing for TAVT-18 (sirolimus) powder for oral solution in TSC infants (N=5) that would then be carried forward to inform appropriate initial dosing, dosing frequency, and dosing adjustments for the second stage—a randomized, double-blind, placebo-controlled multi-site trial design—to evaluate the safety and efficacy of early sirolimus treatment to prevent epilepsy in TSC infants until 12 months of age (N=60). However, with the elimination of the planned second stage which has now been replaced by STOP2B: TSC-STEPS, the study design now consists of a single stage, phase I clinical trial design only. Subjects will be between 0-6 months of age at time of treatment initiation and meet clinical and/or genetic diagnostic criteria for TSC and have no prior history of clinical seizures at time of enrollment. Treatment will be continued until subjects reach 12 months of age. The TSC Clinic at Cincinnati Children's Hospital Medical Center (CCHMC) will serve as the single clinical site.

Additional key investigators of the study:

- [name] (CCHMC) will direct EEG acquisition and data transfer quality control, processing, and blinded central analysis
- [name] (UNC, Chapel Hill) will direct neuropsychological assessments and data transfer quality control, processing, and blinded central analysis
- [name] [name] (CCHMC) will direct PK/PD sample acquisition and quality control, processing, and blinded central analysis
- [name] (Boston Children's Hospital) will direct dMRI acquisition and data transfer quality control, processing, and blinded central analysis
- [name] (CCHMC) will serve as study biostatistician

Operations will be managed through the Clinical Coordinating Center (CCC) and Data Management Center (DMC) at CCHMC to ensure the optimal scientific rigor, efficient execution and management of the study, and analyses.

An independent medical monitor (MM) and Data Safety Monitoring Board (DSMB) will be established to ensure patient safety is appropriately monitored and prioritized throughout the study.

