### Primary Endpoint Analysis and Statistical Considerations (Efficacy):

The hypothesis is that sirolimus will prevent or delay seizure onset in infants with TSC up to 12 months in age. To evaluate efficacy, we will determine time to seizure onset after treatment initiation in infants treated with sirolimus.

It was originally planned for this analysis to consist entirely of subjects enrolled into Stage 2 (n=60), comparing time to seizure onset between the two groups (treatment vs. placebo). With Stage 2 now eliminated from this protocol, we will instead use a contemporary, prospectively evaluated historical control group (n=32) from our TACERN/TSC-EBS natural history study for comparison (Wu et al. Epilepsia 2019. 60:2428-36), in which infants were similarly enrolled 0-6 months of age and followed until 24 months of age. Instead of time to seizure onset for the comparative analysis, we will use age of seizure onset as the outcome of interest as there was no treatment in the TACERN/TSC-EBS studies to use as a start point. The average age of seizure onset in the TACERN/TSC-EBS control group was 7.4 ±4.4 months. For statistical significance, we will use t-test or Wilcoxon rank sum test for the differences, depending on distribution (parametric vs. nonparametric). In addition, survival analysis will be conducted with statistical comparison between treatment groups utilizing the long-rank test. Seizure frequency, and history of infantile spasms at 12 months of age have been shown to be predictive of long-term neurodevelopmental outcome and seizure control at 24-36 months of age. Therefore, we will similarly compare seizure frequency at 12 months of age using the t-test/Wilcoxon rank sum test and the proportion of subjects who develop infantile spasms (past or current) using Fisher's exact test.

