## 16.2 Study Size and Power Calculations

The original study was powered for the planned enrollment of Stage 2, in which 60 subjects were to be randomized 2:1 for treatment with TAVT-18 (sirolimus) vs. placebo. These power calculations remain valid for STOP2B: TSC-STEPS (CCHMC IRB#2021-0438) that has replaced Stage 2 of the current study. However, with enrollment under the current protocol now limited to Stage 1 only (n=5), this study is no longer powered for definitive analysis and becomes a true pilot study aimed at obtaining preliminary data with regard to potential treatment safety concerns and an estimation of patient variability in treatment response. Analyses for statistical significance will still be carried out with the modifications as outlined above, but it is expected that unless the treatment effect size is very large compared to a similarly matched historical cohort from the TACERN/TSC-EBS study, statistical significance will not be achieved with such a low number of treated individuals in this study. Nonetheless, descriptive analysis as a pilot study using sirolimus (TAVT-18) in a patient population (TSC infants 0-12 months of age) that has hereto never previously been studied in a prospective fashion still has immense scientific and clinical value. Furthermore, should the TAVT-18 sirolimus formulation be further developed as a potential clinical treatment for this indication, the descriptive statistics will provide essential data for estimating potential treatment effect size and interpatient variability values that will prove essential for determining study size and study power.

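### The multivariable Cox and logistic models planned for the EEG secondary endpoint cannot be reliably estimated from five treated infants

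*Combined protocol and SAP*

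**What the plan says.** In section 16.1, under the secondary endpoints, the association between epileptiform discharges and the primary efficacy outcomes is to be studied by several methods. Two matter here. One is a "multivariable Cox proportional hazard analysis to assess the contribution of concurrent clinical or genetic variables on the response to treatment". The second method is described there as "logistical regression analysis to determine the strength of associations". The text names no covariates, analysis population, minimum number of events or small-sample method.

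The design around this text has changed. Section 5 states that "the study design now consists of a single stage, phase I clinical trial design only". Section 16.2 recalls that "60 subjects were to be randomized 2:1 for treatment with TAVT-18 (sirolimus) vs. placebo", and then describes the present study "with enrollment under the current protocol now limited to Stage 1 only (n=5"). For the primary efficacy analysis, section 16.1 responds to the change: "we will instead use a contemporary, prospectively evaluated historical control group (n=32"). The secondary endpoint text has no matching statement.

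Section 16.2 concedes that the study is a pilot and that significance is unlikely unless the effect is very large. It nevertheless keeps the significance analyses, as modified, and says nothing about whether the multivariable models can be fitted.

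**The concern.** A regression coefficient has a finite maximum-likelihood estimate only if the data overlap enough across covariate values and outcomes. With five infants they usually do not. Software then stops, warns, or prints a very large coefficient that reflects where the iterations ended. Where a fit does exist, its interval is too wide to use.

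This differs from low power. The caveat in section 16.2 prepares the reader for non-significant results. It does not prepare the reader for estimates that do not exist. Because the covariates are unnamed, the analyst could also end up reporting whichever combination happens to converge. At stake is a secondary EEG analysis; no primary endpoint and no infant's safety depends on it.

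**Working it through.** **Inputs from the document**
- Treated infants: 5 (section 16.2).
- Historical controls: 32, with no study treatment (section 16.1).
- Seizure rate: "70% of diagnosed infants will develop seizures in the first year of life" (section 2). The treated rate is not stated, so I use 35% to 70% as an assumed range.
- Control spread: "The average age of seizure onset in the TACERN/TSC-EBS control group was 7.4 ±4.4 months" (section 16.1).

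The plan gives no event count or power figure for these models, so there is none to reproduce.

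**The plan's caveat on effect size.** Assume a common SD of 4.4 and two-sided alpha 0.05. The standard error is 4.4 × √(1/5 + 1/32) = 2.12 months. The difference detectable with 80% power is (1.96 + 0.84) × 2.12 = 5.9 months, or 1.35 SD. The caveat is right, but it concerns power.

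**Expected events.** 5 × 0.70 = 3.5; 5 × 0.35 = 1.75. A discharge term plus two covariates makes three parameters: 3.5/3 = 1.2 and 1.75/3 = 0.6 events per parameter.

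**One balanced binary covariate, logistic model (exact).** The covariate has prevalence 0.5 and is independent of outcome. A finite non-zero odds ratio needs all four cells of the 2×2 table occupied. With five infants one cell holds two and the others one each, so the probability is 60 × p₁p₂p₃p₄.
- Event rate 70%: 60 × 0.35² × 0.15² = 0.165, so 83% have no finite non-zero odds ratio. Of all tables, 31% give an infinite ratio, 31% zero and 22% are undefined.
- Event rate 50%: 60 × 0.25⁴ = 0.234, so 77%.
- Event rate 35%: 60 × 0.175² × 0.325² = 0.194, so 81%.

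**Several covariates (simulation).** Seizure times are exponential, censored at 12 months, with no covariate effects. Assumed covariates: discharges 50%, a genetic variable 70%, age uniform over 0 to 6 months. Each dataset was tested for separation (logistic) or monotone likelihood (Cox). There were 1,500 datasets per setting. Percentage with a finite estimate, at event rates 35% / 50% / 70%:

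| Covariates, n = 5 | Cox | Logistic |
|---|---|---|
| 1 binary | 30.0 / 43.9 / 59.2 | 19.4 / 23.4 / 16.5 (exact) |
| 2 binary | 6.8 / 14.1 / 22.7 | 2.7 / 3.5 / 2.0 |
| 2 binary + age | 3.7 / 6.3 / 13.9 | 0.7 / 1.4 / 0.7 |
| 2 continuous | 40.3 / 55.5 / 74.0 | 27.9 / 30.8 / 24.1 |
| 3 continuous | 11.1 / 20.6 / 30.5 | 5.7 / 7.0 / 5.1 |

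A repeat with 6,000 datasets gave 7.8 / 12.6 / 21.7 for the two-binary Cox model.

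**Precision when a fit exists.** For the two-binary Cox model the median standard error of the log hazard ratio is about 1.43. The upper 95% limit is then about exp(2 × 1.96 × 1.43), or roughly 270 times the lower. With 60 infants, 99% to 100% of these fits are finite and the ratio is about 3.5 to 6.

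**Pooling with the controls.** There are 37 infants and 32 × 0.70 + 1.75 = 24.15 to 32 × 0.70 + 3.5 = 25.9 events (300 datasets per setting). With treatment and two binary covariates as main effects, the Cox model is finite in 90% to 99% and the logistic in 78% to 88%. Adding treatment interactions with both covariates lowers this to 9% to 46% (Cox) and 1% to 2% (logistic).

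**The case against.** The strongest reply is that the controls may be meant to enter. The primary efficacy analysis uses them, and a pooled main-effects model would often be estimable. That stands. A reader might infer that pooling cannot help at all; the document does not support that, since the discharge-outcome association could well be estimated in 37 infants. But the document does not say that the controls enter these models, nor that their EEG and genetic data will be available. What modifies response to sirolimus can be learned only from infants who received it.

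Four other stronger readings should be set aside.
- A reader might infer that the models can never be fitted. With one binary covariate a Cox fit is finite in about 30% to 60% of datasets, and with two continuous covariates in 40% to 74%. The accurate claim is that they cannot be reliably estimated.
- A reader might take both regressions to concern effect modification. Only the Cox model is tied to response to treatment, and even there covariate adjustment is a possible reading. The logistic model fails on sparse data alone.
- A reader might infer that the text is a leftover from the 60-infant design. That is plausible, but no section says so.
- A reader might infer that the coefficients will drive later sample sizes. Section 16.2 gives that role to the descriptive statistics, and only if the formulation is developed further.

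The pilot caveat limits the harm. It does not address estimability, and it keeps the inferential analyses.

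**Conclusion.** The point holds in this limited form: applied to the five treated infants, the planned multivariable Cox and logistic models would usually give no finite estimate, or one too imprecise to use. The one-covariate odds-ratio figures (83% and 77%) are exact for a balanced covariate independent of outcome. The multivariable figures (Cox 7% to 23%, logistic 2% to 4% with two binary covariates) rest on assumed prevalences, exponential times, no covariate effects and event rates of 35% to 70%. Two continuous covariates are kinder to the Cox model, but the logistic model still fails in about 70% of datasets or more. Whether a pooled main-effects model is intended, and feasible, cannot be settled from the document.

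**What to change.** In the secondary endpoint text of section 16.1, remove the multivariable Cox and logistic regressions for the treated infants. Replace them with per-infant listings or timelines of EEG findings, genotype, trough levels and seizure onset, plus counts with exact intervals. State that no inference on effect modification will be made.

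If a model is kept, limit it to one prespecified main-effects model pooled with the 32 controls, using a penalized method, a named covariate and a minimum event count. Make it conditional on control EEG and genetic data being available, and label it exploratory.

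The cost is SAP wording only. The downside is that no modelled covariate effect on response is reported; five infants could not supply a usable one.

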### Encephalography (EEG)

Encephalography (EEG) with video is recommended at the time of TSC diagnosis and as clinically indicated thereafter for surveillance of seizure risk and response to treatment. EEG (60 minutes, included extended epochs of both wake and sleep states) are scheduled to be acquired at every visit, but at minimum will be performed at baseline and at end of treatment (12 months). Sites in this network will utilize identical EEG acquisition protocols and procedures established by the TSC Clinical Research Consortium that are designed to yield comparable results across different equipment platforms. Recordings will utilize 21 gold-plated electrodes placed according to the International 10-20 system with a digital sampling rate at a rate of 2000Hz with no filters, displayed at an effective time scale of 30 mm/sec with 1Hz low frequency and 70Hz high frequency display filters on the left screen, and on the right screen a maximum time scale of 100 mm/sec, 30Hz low frequency filter (high pass) and 100Hz high frequency filter (low pass). These parameters were designed to yield comparable data on Stellate, Nihon-Kohden, XLTEK/Natus EEG systems throughout the consortium. Any additional EEG obtained for clinical purposes between scheduled visits will also be collected for research analysis. The digitized EEG source data will be transferred to CCHMC for central processing and analysis.

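### The 512-point FFT in the quantitative EEG plan cannot give 0.5 Hz resolution and also reach the ripple and fast-ripple bands; at the 2000 Hz recording rate only the FFT length needs to change

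*Combined protocol and SAP*

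**What the plan says.** The quantitative EEG settings are in Section 16.1, under the secondary endpoint analysis. The FFT is defined by "The 512-point FFT is calculated for artifact-free two-second epochs with a rectangular window", with "0.5 Hz overlap at the limits of the band" and "yielding a frequency resolution of 0.5Hz". The text then says "Power will be calculated in six frequency bands" and lists seven: delta (0.5-4 Hz), theta (4-8), alpha (8-12), beta (12-20), gamma (30-50), and finally "ripple frequencies (100-250Hz), and fast ripple frequencies (250-500Hz").

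The documents state two EEG sampling rates. Section 11.6 (Encephalography) sets acquisition "with a digital sampling rate at a rate of 2000Hz with no filters", and adds that "The digitized EEG source data will be transferred to CCHMC for central processing and analysis". Section 16.1 gives a lower rate, but for a different purpose: "EEG data for conventional analysis (interictal and ictal epileptiform activity) will be sampled at 500 samples/channel/second". No rate is stated for the quantitative analysis, and no down-sampling step before it is described.

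**The concern.** For an FFT, the sampling rate, number of points, epoch length, resolution and highest usable frequency are tied together. Once two are fixed, the rest follow. The plan fixes four (points, epoch, resolution and highest band), and they do not appear to agree.

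If they do not, the analyst has to depart from the text somewhere. Keeping 512 points and 0.5 Hz gives up the fast-ripple band and most of the ripple band. Keeping 512 points and the high bands gives up the stated resolution, on which the lower bands and the 0.5 Hz band-edge overlap depend. The high bands matter to the rationale: Section 2 cites high-frequency oscillations as possible markers of epileptogenicity in this disease. Section 16.1 also plans biomarker comparisons with the vigabatrin prevention trial, which need a spectral setting that others can reproduce.

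**Working it through.** **Inputs.** FFT length N = 512, epoch T = 2 s, resolution 0.5 Hz and highest band edge 500 Hz (all Section 16.1). Sampling rates: 2000 Hz for acquisition (Section 11.6) and 500 samples/s for conventional EEG only (Section 16.1). The rate for quantitative EEG is not stated, so 256 to 2000 samples/s was examined.

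**Formulas.** With sampling rate fs: samples in an epoch = fs × T; resolution = fs / N; highest usable frequency (Nyquist) = fs / 2.

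**1. Reproducing the plan's own figure.** 512 points filling 2 s means fs = 512 / 2 = 256 samples/s. Resolution is 256 / 512 = 0.5 Hz, as stated. So three of the four settings agree at this rate. The ceiling, however, is 256 / 2 = 128 Hz. Ripple coverage is (128 − 100) / 150 = 18.7%, and fast-ripple coverage is 0.

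**2. Test that needs no assumed rate.** Content up to 500 Hz needs fs of at least 1000 samples/s. At 0.5 Hz resolution, N = fs / 0.5, so N is at least 1000 / 0.5 = 2000. The stated 512 falls short whatever the rate.

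**3. Settings at each candidate rate.**

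| Reading | Span of FFT | Resolution | Ceiling | High bands |
|---|---|---|---|---|
| 512 points at 256 samples/s | 2 s | 0.5 Hz | 128 Hz | ripple 28 of 150 Hz; fast ripple none |
| 512 one-sided bins (1024 points at 512 samples/s) | 2 s | 0.5 Hz | 256 Hz | ripple complete; fast ripple 6 of 250 Hz (2.4%) |
| 512 points at 500 samples/s | 1.024 s | 0.98 Hz | 250 Hz | ripple to its upper edge; no fast ripple above that edge |
| 512 points at 2000 Hz | 0.256 s | 3.906 Hz | 1000 Hz | both complete |
| 4000 points at 2000 Hz | 2 s | 0.5 Hz | 1000 Hz | both complete |

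**4. What 512 points at 2000 Hz would mean.** The FFT covers 512 / 4000 = 12.8% of the epoch. Resolution is 3.906 / 0.5 = 7.8 times coarser than stated. Bins fall at 3.91, 7.81 and 11.72 Hz, so delta, theta and alpha have one bin each; at 0.5 Hz they would have 8, 9 and 9, counting both edges. Averaging the seven whole 512-point segments that fit in an epoch (3584 of 4000 samples) uses more of the data but leaves resolution at 3.906 Hz. The 0.5 Hz overlap is then 0.5 / 3.906 = 0.128 of a bin, about an eighth.

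**5. Dropping the 512.** At 2000 Hz, 2 s gives 4000 samples, 2000 / 4000 = 0.5 Hz and a 1000 Hz ceiling. The epoch, the resolution, the overlap and all seven bands then agree.

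**The case against.** The best case for the plan is that 512 is not the wrong figure. Within its own sentence it fits two seconds and 0.5 Hz exactly, at 256 samples/s, and those settings cover the five bands up to 50 Hz. On that reading the plan holds a sound low-frequency specification, and what is missing is a separate rate and FFT length for the two high bands. The count of six against seven listed bands shows that the band list has at least one slip of its own. Silence on down-sampling also proves little: conventional EEG goes from 2000 Hz to 500 samples/s with no reduction step described.

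Much of this stands. The documents do not confirm the rate for quantitative EEG, so they do not settle which figure was intended, and delta to gamma can be run as written at 256 samples/s. It does not remove the conflict, because the text applies one FFT specification to all seven bands and no sampling rate satisfies it. Of the two rates the documents give, only 2000 Hz reaches 500 Hz, and there the 512 is the one setting that does not fit.

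**Conclusion.** The concern holds, at minor severity. No sampling rate reconciles 512 points, two-second epochs, 0.5 Hz resolution and bands up to 500 Hz. The cost of following the text is either all of fast ripple and 81% of ripple (122 of 150 Hz), or a resolution of 3.9 Hz in place of 0.5 Hz.

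The inconsistency itself needs no assumption. That correcting the FFT length alone is enough assumes that the quantitative analysis uses the 2000 Hz recordings.

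The consequence is small. EEG processing is central (Sections 5 and 11.6), so this is one setting and not a source of differences between sites. The output is secondary and descriptive in a study that Section 16.2 calls a pilot, with five infants. Band power is not among the EEG measures named in Section 4.2. The analysis can be rerun from the source recordings, and no primary, safety or dosing conclusion depends on it.

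**What to change.** Either of two changes would make the specification consistent.

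- **Simplest:** replace the 512-point FFT with one over the full two-second epoch at the 2000 Hz acquisition rate (4000 points, 0.5 Hz resolution, 1000 Hz ceiling). State that the data are not reduced to 1000 samples/s or below before the ripple and fast-ripple calculations; at exactly 1000 the 500 Hz band edge is the Nyquist frequency itself. State also that the 500 samples/s rate for conventional EEG is not used for these bands.
- **Alternative:** keep 512 points, state that the data are down-sampled to 256 samples/s for the five bands up to 50 Hz, and give a separate sampling rate and FFT length for the two high bands.

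In both cases, change the band count from six to seven; this is editorial.

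The cost is a wording change and one software setting, or two under the alternative. Recording at 2000 Hz without filters is already planned, so no new data are needed.
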